## 2 Trial Identification:

ClinicalTrials.gov number: Application pending

## 3 Introduction and Rationale

### 3.1 Molluscum Contagiosum

Molluscum contagiosum (MC) is a common skin infection in children caused by a poxvirus that is transmitted through direct skin-to-skin contact, fomites, or autoinoculation (1). In adults, it is less common and often sexually transmitted, with a greater predisposition for immunocompromised patients (2). MC is characterized by asymptomatic, discrete, smooth, flesh-colored, dome-shaped papules with central umbilication (3). In immunocompetent adults, lesions are usually confined to the genital area and adjacent regions of the skin (1). In patients with immunocompromised conditions, lesions can be widespread and even disfiguring (1,2,4,5). MC in immunocompromised patients are often resistant to conventional treatment used to treat those in immunocompetent patients (5). There is an unmet need for improved therapies for treatment of MC in immunocompromised patients.

### 3.2 Experience with Investigational Product

Ingenol mebutate (Picato, LEO Pharma), a macrocyclic diterpene ester, is the active agent in the sap of the plant *Euphorbia peplus*, which is known for its therapeutic effects in common skin lesions, including cancerous lesions (6). Preclinical studies have demonstrated that ingenol mebutate has a dual mechanism of action: rapid lesion necrosis and specific neutrophil-mediated, antibody-dependent cellular cytotoxicity (7,8). Picato was originally licensed as a field therapy for actinic keratosis (6). It has also been reported to be effective against anogenital warts and MC in immunocompetent patients (9,10). Picato gel is available in two strengths, 0.015% once daily for the face and scalp and 0.05% once daily for the trunk and extremities. The safety of all doses studied so far has been with an acceptable benefit-risk profile and no major safety concerns have been identified. Possible risks associated with use of Picato gel are summarized in Section 10.3.

### 3.3 Trial Rationale

The purpose of this trial is to provide evidence of the efficacy and safety of Picato gel in the treatment of subjects with MC in the setting of immunocompromised status. The trial duration is 24 weeks.

The primary efficacy endpoint is complete clearance of MCs in the treatment area at Week 4, with a secondary efficacy endpoint of partial clearance in the treatment area at Week 4. Assessment of long-term efficacy will be based on the percentage of subjects who sustain complete clearance of MCs in the treatment area at Week 24 and the percentage of subjects who clear MCs outside of the treatment area at Week 24.

Safety and tolerability endpoints will include development of local skin reactions (LSRs) including erythema, flaking/scaling, crusting, swelling, vesiculation/pustulation, and erosion/ulceration, patient's global satisfaction as measured by Treatment Satisfaction Questionnaire of Medication (TSQM) v.9, and health-related quality of life (HQoL) as measured by EQ-5D-5L questionnaire.

For evaluation of safety, all subjects will be followed for AEs and Serious Adverse Events (SAEs) occurring in the treatment area from the signing of the informed consent form through completion of the study.

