### 4.2 Secondary Objectives

- To evaluate the efficacy of Picato gel (0.05% and/or 0.015%) on patient's global satisfaction and health-related quality of life
- To evaluate the safety and tolerability of Picato gel (0.05% and/or 0.015%) in MC in immunocompromised patients when applied topically once nightly for three consecutive nights
- To evaluate the long-term efficacy of Picato gel (0.05% and/or 0.015%) in MC in immunocompromised patients over a 24-week period

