### **9.1 Collection of Adverse Events**

All AEs and SAEs must be collected from the signing of the informed consent form and until the last follow-up visit at Week 24.

Abnormal findings observed at screening do not constitute AEs, but must be recorded in medical history.

For AEs recorded on the day starting treatment, it should be specified whether the AE started prior to or after first application of IP.

AEs must be assessed by medically qualified personnel. A qualified physician must conduct all dermatologic examinations, LSR and AE evaluation of the treatment area.

At all visits, the subject will be asked a non-leading question by the (sub)investigator such as: “How have you felt since I saw you last?” No specific symptoms should be asked for. It is important that the (sub)investigator also observes the subject for any changes not reported by the subject and records these changes.

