### **9.2 Reporting of Adverse Events**

AEs reported by the subject or observed by the (sub)investigator must be recorded on the AE form and should be described in the following manner:

The AE term will be in precise English medical terminology (i.e. not necessarily the exact words used by the subject). Whenever possible, a specific diagnosis should be stated (e.g. allergic contact dermatitis).

For AEs the location must be part of the AE description and may be described as “in the treatment area”, “outside the treatment area” or “non-cutaneous”.

The duration of the AE must be reported by the start date and stop date of the event. In addition, it must be recorded whether the AE started prior to start of trial medication.

AEs must be classified in terms of severity, causality and outcome according to the definitions in Appendix 4: Classification of Adverse Events.

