### **9.3 Additional Reporting Requirements for Serious Adverse Events**

Any SAE must be reported to LEO on the (paper) SAE Form – Clinical Trials within 24 hours of first knowledge. This report should contain an assessment of available information on seriousness, severity, causal relationship to the IP or trial procedure, the action taken, the outcome to date, and a narrative description of the course of the event.

Any LSR classified as an SAE must be added to the AE form and in addition reported to LEO on the SAE form.

The completed SAE form must be scanned and e-mailed to the local safety contact person of LEO Entity using the following e-mail address [[contact]](mailto:[contact]) stating the following reference in the e-mail subject field: “PV report – IIS-PICATO-1386”.

It may be relevant for the (sub)investigator to enclose other information with the SAE form, such as reports of diagnostic procedures, hospital records, autopsy reports, etc.

Additionally, LEO may request further information in order to fully assess the SAE. The (sub)investigator must forward such information to LEO upon request by e-mail (see contact details above).

The investigator must notify the local Institutional Review Boards (IRBs)/Independent Ethics Committees (IECs) of SAEs as required by current applicable legislation for the concerned country, however no later than fifteen (15) days after becoming aware of the case.

In addition, the Sponsor shall forward to the LEO local safety contact person any received customer complaints related to any LEO produce, and ensure that all Adverse Events and customer complaints are described in the Final Report.

Causally related SAEs occurring after the completion of the clinical trial including any protocol required post-treatment follow-up period should not be routinely sought or collected. However, such events should be reported to LEO ([[contact]](mailto:[contact])) if the (sub)investigator becomes aware of them.

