### **9.4 Follow-up for Final Outcome of Adverse Events**

During the trial, the investigator should follow up for final outcome on all AEs (including SAEs). Once a subject has completed the clinical trial, LSRs as well as AEs classified as possibly or probably related to

the IP, that are deemed clinically significant, should be followed for 2 months or until final outcome has been established, whichever comes first.

SAEs must be followed up until a final outcome has been established, i.e. the follow-up may continue beyond the end of the clinical trial.

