### 17.2 Serious Adverse Event Definition

A serious adverse event (SAE) is any untoward medical occurrence that

- results in death
- is life-threatening
- requires inpatient hospitalization or prolongation of existing hospitalization. Planned hospitalization or planned prolonged hospitalization do not fulfill the criteria for being an SAE but should be documented in the subject's medical record.
- results in persistent or significant disability/incapacity
- is a congenital anomaly/birth defect
- is a medically important condition. Events that may not be immediately life threatening or result in death or hospitalization but may jeopardize the subject or may require intervention to prevent one of the other outcomes listed in the definition above. Examples are intensive treatment in an emergency room or at home for allergic bronchospasm, blood dyscrasias and convulsions that do not result in hospitalization, development of drug dependency or drug abuse

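### Does Section 3.3 restrict the safety evaluation to adverse events in the treatment area?

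*Protocol*

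**What the plan says.** Section 3.3 (Trial Rationale) describes safety follow-up in one sentence: "For evaluation of safety, all subjects will be followed for AEs and Serious Adverse Events (SAEs) occurring in the treatment area". The period runs from consent to study completion.

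The working sections are broader:

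- Section 9.1: "All AEs and SAEs must be collected from the signing of the informed consent form and until the last follow-up visit at Week 24".
- Section 9.2 makes location part of each AE description, which "may be described as “in the treatment area”, “outside the treatment area” or “non-cutaneous".
- Section 9.3: "Any SAE must be reported to LEO on the (paper) SAE Form". The sponsor must also "ensure that all Adverse Events and customer complaints are described in the Final Report".
- Section 9.4: during the trial "the investigator should follow up for final outcome on all AEs (including SAEs").
- Appendix 3, Section 17.2: "A serious adverse event (SAE) is any untoward medical occurrence that" meets one of the listed seriousness criteria. The AE definition in 17.1 is equally free of any location limit.

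The safety objective in Section 4.2 is likewise unrestricted: "To evaluate the safety and tolerability of Picato gel (0.05% and/or 0.015%) in MC in immunocompromised patients".

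**The concern.** The two scopes cannot both be literally right. If the treatment-area limit applied, systemic SAEs would drop out of the safety evaluation, and every subject in this trial is immunocompromised. So would periorbital or eyelid edema. Section 10.3.1 anticipates these events after treatment on the face or scalp, yet periorbital skin cannot be part of the treatment area (exclusion criterion 1 in Section 7.3; Section 10.2).

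Section 3.3 also carries some weight of its own. Sections 5.1 to 5.3 list only clearance and patient-reported endpoints, so 3.3 is where the protocol names its safety and tolerability endpoints. Someone defining a safety summary might look there first. With 10 subjects (Section 6.2), one omitted SAE would alter the safety picture.

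**Working it through.** No arithmetic applies. The protocol states no AE or SAE frequencies, so the check is a comparison of the passages.

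**1. Is there a reading under which the passages agree?** Not fully.

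- If the location phrase attaches only to SAEs, it still conflicts with 9.1, 9.3 and Appendix 3. Those criteria include death and hospitalization, which do not belong to an area of skin.
- Section 9.1 mentions AE evaluation of the treatment area, but that sentence says who must carry out the evaluation, not which events count.
- The post-trial limit in 9.4 depends on event type, relatedness and clinical significance, not on location.

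The inconsistency therefore stands as a matter of wording.

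**2. Which text governs what is done?**

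| Step | Governing text | Location limit |
|---|---|---|
| Assessment at visits | Section 8.1: AEs marked at all 16 numbered visits | None |
| How to assess and record | Section 8.11: refers to Section 9 | None |
| Collection, consent to Week 24 | Section 9.1 | None |
| Description of each event | Section 9.2: three location categories, two of them away from the treatment area | None |
| SAE reporting | Section 9.3: any SAE, within 24 hours | None |
| Follow-up to outcome | Section 9.4 | None |
| After withdrawal | Section 7.6: refers to Section 9 | None |
| Final Report | Section 9.3: all AEs; Section 12: the whole study | None |

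The true counterpart of the sentence in 3.3 is 9.1. Both describe watching subjects for events, and over the same period, since 3.3 gives a trial duration of 24 weeks and 9.1 ends at the Week 24 visit. Section 9.4 deals with following known events to their outcome, so it confirms the wider scope but is not the direct comparison.

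**3. Does the narrow reading make sense within the protocol?** It does not.

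- The visit question in 9.1 is a general one about how the subject has felt and is not tied to the treated skin.
- Under 8.12, the expected reactions inside the treatment area are graded on the local skin reaction (LSR) scale, and only responses that do not fit that scale become AEs. A treatment-area limit would shrink the AE set to that remainder plus any LSR serious enough to be an SAE.
- Two of the three categories in 9.2 would have no purpose in the safety evaluation.

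This points to a drafting slip and not to an intended restriction.

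**4. Would the named examples be lost?** Section 10.3.1 says that clinically significant periorbital or eyelid swelling is recorded as an AE, and 9.3 then puts it in the Final Report. Swelling that spreads beyond a treated facial area can also be graded 4 on the scale in Appendix 2. A systemic SAE is collected under 9.1, reported under 9.3 and followed to its outcome under 9.4.

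**The case for a change.** The best argument for acting is that the protocol states a wrong scope outright, in the one place where it names safety endpoints, and that removing a single phrase would cost nothing. The mismatch and the low cost are both granted.

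What does not stand is the consequence. The endpoint sentence in 3.3 is worded as a non-exhaustive list (LSRs, treatment satisfaction, quality of life) and does not mention AEs. The next sentence describes what subjects are followed for and does not define an analysis set. No passage says that a safety summary takes its scope from 3.3. A Final Report limited to treatment-area events would breach 9.3. What remains is some other document, such as a publication or an analysis table, whose author follows 3.3 and disregards Section 9. AE table scope is normally set in a statistical analysis plan, which is not shown here, so no harm can be inferred from its absence.

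**Conclusion.** This is a clerical inconsistency between a background sentence and a consistent set of operative rules. Its extent is one phrase in 3.3 against Sections 9.1 to 9.4 and Appendix 3. No effect on data collection, SAE reporting, follow-up or the Final Report is shown, and none can be quantified from the protocol. Aligning the phrase with 9.1 would be tidy editing but would change nothing that the trial does or concludes.

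The conclusion rests on two assumptions: staff work from Section 9, as 8.11 directs, and the safety results are compiled from the AEs recorded there, as the Final Report duty in 9.3 requires. On that footing, no change to the plan is called for.

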### 3.4 Justification for Dose

The selected dose for this trial is topically administered Picato 0.05% gel. The Picato gel 0.05% dose was chosen based on principal investigator's extensive clinical experience in treating immunocompromised patients with MC using the higher concentration. For subjects who cannot tolerate Picato 0.05% gel as judged by the sub(investigator), the lower concentration of 0.015% will be used.

### 3.5 Ethical Considerations

No children or other vulnerable subjects incapable of giving informed consent will be enrolled in this clinical trial. Furthermore, women who are pregnant, breastfeeding, or trying to become pregnant will not be enrolled in this clinical trial. Women of child-bearing potential have to agree to use an effective method of contraception to prevent pregnancy during the clinical trial. In addition, all female subjects of child-bearing potential will have a pregnancy test performed before, during and at End of Treatment to ensure that no fetuses are exposed to the IMP.

Altogether, the risks associated with participating in this clinical trial are considered very low and outweighed by the benefit of a potential future treatment option for MC in immunocompromised patients.

In accordance with the current version of the International Council for Harmonization (ICH) Good Clinical Practice (GCP) guidelines, qualified medical personnel employed by LEO Pharma A/S and Center for Clinical Studies will be readily available to advise on trial-related medical questions.

In conclusion, the trial design chosen for this efficacy and safety trial on Picato is regarded as ethically justified and adherent with ethical requirements.

## 4 Trial Objectives

### 4.1 Primary Objective

- To evaluate the efficacy of Picato gel (0.05% and/or 0.015%) in MC in immunocompromised patients when applied topically once nightly for three consecutive nights

### 4.2 Secondary Objectives

- To evaluate the efficacy of Picato gel (0.05% and/or 0.015%) on patient's global satisfaction and health-related quality of life
- To evaluate the safety and tolerability of Picato gel (0.05% and/or 0.015%) in MC in immunocompromised patients when applied topically once nightly for three consecutive nights
- To evaluate the long-term efficacy of Picato gel (0.05% and/or 0.015%) in MC in immunocompromised patients over a 24-week period

## 5 Trial Endpoints

### 5.1 Primary Endpoint

- Complete clearance at Week 4, defined as no clinically visible MCs in the treatment area

### 5.2 Secondary Endpoints

- Partial clearance at Week 4, defined as at least 50% reduction in the number of clinically visible MCs in the treatment area

- Percentage of subjects who sustain complete clearance of MCs in the treatment area at Week 24
- Percentage of subjects who clear MCs outside of the treatment area at Week 24

### 5.3 Other Endpoints

#### Patient reported outcomes

- TSQM v.9, Global Satisfaction
- EQ-5D-5L, Index and Health Status

## 6 Trial Design

### 6.1 Overall Trial Design

This is a case series in subjects with MC in the setting of immunocompromised status.

Subjects will attend a screening visit where they will be assessed for eligibility. Eligible subjects will complete the baseline visit on the same day as the screening visit. There will be no washout period in this trial. Eligible subjects will be assigned Picato 0.05% gel at Visit 1. Two boxes, each containing 2 tubes of Picato 0.05% gel, will be dispensed to each subject at Visit 1. Subjects should use a new tube for each treatment day.

All subjects will apply gel using a cotton swab for 3 consecutive nights at home (Day 0, Day 1, Day 2). Subjects will be followed for 4 weeks after the first application of IP at Day 0 (3-day treatment period including 4-week follow-up period).

Subjects who have not achieved complete clearance in the treatment area at Week 4 will receive a second course of treatment for 3 consecutive nights (Day 28, Day 29, Day 30). These subjects will be followed for another 4 weeks after the first application of the second course of IP at Day 28 (3-day treatment period including 4-week follow-up period).

Subjects who have not achieved complete clearance in the treatment area at Week 8 will receive a third course of treatment for 3 consecutive nights (Day 56, Day 57, Day 58). These subjects will be followed for another 4 weeks after the first application of the third course of IP at Day 56 (3-day treatment period including 4-week follow-up period).

Residual erythema may be present and will not be considered lesions. All subjects will have follow-up visits at Week 16, Week 20, and Week 24 from the first application of IP.

The number of MCs within the treatment area and outside of the treatment area will be counted at every visit. The treatment area may be one contiguous area or up to two non-contiguous areas. The total treatment area should not exceed 100 cm^2. Picato gel should be applied at least 2 hours before sleeping and be allowed to dry for at least 15 minutes after application. For subjects who cannot tolerate Picato 0.05% gel as judged by the sub(investigator), the lower concentration of 0.015% will be used. The treatment area will be identified and tracked with a transparency, which will capture both anatomical landmarks and the treatment area, to orient the patient and investigator to the treatment area over time.

### 6.2 Sample size

In total 10 subjects will be enrolled in the trial and all subjects will received Picato gel in either 0.05% or 0.015% concentration depending on subject's tolerability.

## 7 Trial Population and Withdrawal

### 7.1 Subject Eligibility

The (sub)investigator should only enroll subjects who meet all eligibility criteria, are not put at undue risk by participating in the trial and can be expected to comply with the protocol.

The subject's eligibility for the clinical trial must be checked according to the inclusion and exclusion criteria at visits specified in the "Schedule of Trial Procedures" (see Section 8.1)

Re-screening is allowed if the visit window cannot be complied with for practical reasons. Re-sampling or re-screening is not allowed if the subject has failed one of the inclusion or exclusion criteria.

### 7.2 Inclusion Criteria

1. Signed and dated informed consent has been obtained.
2. Male or non-pregnant female at least 18 years of age.
3. Subject must have an immunocompromised condition due to use of immunosuppressive therapies for cancer or autoimmune disease treatment or prevention of organ transplant rejection or due to an inherited condition that affects the immune system.
4. Subject has at least 10 clinically typical, visible and discrete MCs within a treatment area on either the face and/or trunk. Treatment area is defined as either:
  - One contiguous treatment area of at most 100 cm^2
  - Two non-contiguous treatment areas totaling at most 100 cm^2
5. Subject must be willing to forego any other treatments of MC on the face and/or trunk, including tanning bed use and excessive sun exposure, throughout the duration of the trial.
6. Subject is willing and able to participate in the study as an outpatient, making frequent visits to the study center during the treatment and follow-up periods, and to comply with all study requirements.
7. Female subjects of childbearing potential\* must have a negative urine pregnancy test prior to trial treatment.

\* A female is defined as not being of child-bearing potential if she is postmenopausal (at least 12 months with no menses without an alternative medical cause prior to screening) or surgically sterile (hysterectomy, bilateral salpingectomy or bilateral oophorectomy).

8. Female subjects of childbearing potential must be willing to use effective contraception at trial entry and until the last follow-up visit at Week 24.

Effective contraception is defined as follows:

- Abstinence (when this is in line with the preferred and usual life style of the subject).
- Vasectomized partner (given that the subject is monogamous).
- An intrauterine device.
- Double barrier method defined as condom in combination with diaphragm
- Hormonal contraceptive (oral hormonal birth control, estrogenic vaginal ring, percutaneous contraceptive patches, implants and injectables) for at least one menstrual cycle prior to enrollment.

